5.2 Recruitment Methods

Participants:

The study includes 160 Veterans age 60-95 years (2 treatment conditions x 10 groups x 8 Veterans = 160) with chronic musculoskeletal pain. Veterans are recruited from outpatient clinical sites at West Los Angeles Veterans Affairs Medical Center (WLA), the largest VA Medical Center on the West Coast. We have already partnered with several clinical sites, including Geriatric Psychiatry, Geriatrics, Chronic Pain, Interventional Pain, Women's, and Primary Care Clinics, for our pilot, and plan to use these sites for this project as well. In our pilot, we were able to recruit 48 participants from our clinical sites in 30 weeks. For the proposed trial we have a similar recruitment schedule of approximately 1-2 Veterans per week, in order to complete all treatments and 6-month follow-ups by the end of Year 4, leaving Year 5 for data clean-up and analysis. The schedule in Table 1 indicates recruitment goals for the duration of the study.

Table 1: Enrollment for Each Year	Year 1	Year 2	Year 3	Year 4	Year 5
Screening, Baseline Assessments, EAET, Post-Treatment and 6-month Follow-Up Assessments	24	24	16	16	-
Screening, Baseline Assessments, CBT, Post-Treatment and 6-month Follow-Up Assessments	24	24	16	16	-

Recruitment and Screening Procedures:

Approved clinician and patient flyers are distributed to clinic staff in participating programs (see attached). Before clinic, a medical chart review is performed to determine whether potential Veteran participants meet basic inclusion/exclusion criteria. Clinicians not associated with the study will passively recruit patients by handing them a flyer and referring them to the research team. No Veteran is approached by research staff without having previously agreed to such contact with his/her clinician.

In addition, we will screen additional medical charts using a VA Data Warehouse generated list of veterans aged 60 and older, who carry a diagnosis of low back pain, and are actively receiving care from a VA PCP. Patients identified as eligible this way will be mailed a letter and a flyer about the study. Only patients who reach out to the research team will be considered for enrollment in the study and will not be contacted otherwise.

Finally, we post flyers on VA bulletin boards and at identified locations in the aforementioned clinics, and prospective Veterans are self-referred to research staff through these flyers. A waiver for consent and documentation of consent for recruitment/screening only is being sought from the IRB. Patients who are unable to give informed consent or have a legal conservator are not included in the study. Only in cases in which a patient's capacity to provide informed consent is questionable (according to the clinician's best judgement) will they be required to complete the UCLA Capacity for Consent Form to determine whether they may be included in the study. Patients who have assigned payees are compensated accordingly.

Payments:

After completing the baseline visit (baseline questionnaires), participants will receive \$50. After completing posttreatment questionnaires (Week 9), participants will receive \$50. After completing 6-month follow-up questionnaires (Week 39), participants will receive \$50. Participants receive a check, which is mailed within three weeks of completing the aforementioned study procedures.

Proposed payments are provided for participant time, inconvenience, and transportation to complete research procedures (i.e., questionnaires). Substantial time is needed in order to complete the battery of questionnaires. In addition, driving in Los Angeles can be challenging, with many participants driving a considerable distance. Thus, payments are modest. Participants are not reimbursed for attendance at psychotherapy sessions.

5.3 Informed Consent Procedures

After a Veteran has expressed interest in the study, the PI or other research team member discusses the details of the study, including study procedures, risks, and benefits, with the Veteran by phone or in person. There is an opportunity to ask questions, to have information clarified, and for potential participants to discuss the study with other family members. Standardized demographics and medical history are obtained, as well as psychiatric diagnoses and substance use disorder status. All patients complete the MMSE for screening purposes. If the potential participant meets screening criteria, he/she is invited to enroll as a primary research participant. Those who fail to meet the inclusion/exclusion requirements are thanked for their time. Interested participants come to meet in person with the PI or another research team member to enroll in the study. Consent and HIPAA forms are reviewed with the participant prior to the start of the study. As the need arises, decision-making capacity is assessed by a member of the research team who is a psychiatrist or licensed psychologist. The UCLA Capacity to Consent Form will be used for this purpose. Baseline assessments are then completed. Finally, the Veteran is randomized and scheduled for an individual preparatory session based on treatment assignment (described below).

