5.0 Study Procedures

5.1 Study Design

The project is a randomized superiority trial that compares change in mean pain severity and other outcomes in older Veterans (age 60-95 years) with chronic musculoskeletal pain who receive either Emotional Awareness and Expression Therapy (EAET) or Cognitive Behavior Therapy (CBT). The study includes 160 total participants, 80 randomly assigned to EAET and 80 to CBT. Each participant receives one 90-minute individual session and eight 90-minute group sessions based on the treatment condition (EAET or CBT) to which he/she is randomly assigned. Each EAET group at a time runs concurrently with one CBT group throughout the study. Group sessions consist of small groups of eight Veterans. All participants complete self-report questionnaires on pain, physical and psychiatric symptoms, and emotional well-being at baseline, post-treatment, and 6-month follow-up. Participants also complete self-report questionnaires on emotional approach coping, ambivalence over emotional expression, pain catastrophizing, and adaptive pain coping skills at baseline, post-treatment, and 6-month follow-up. Participants complete a working alliance questionnaire at post-treatment. The data are used to assess the superiority of EAET compared to CBT on change in mean pain severity scores from baseline to post-treatment (primary outcome) and 6-month follow-up and change in other patient-centered outcomes (PCO) from baseline to post-treatment and 6 month-follow-up (secondary outcomes). In addition, the data are used to test mediation of EAET by improved emotion regulation (greater emotional approach coping and decreased ambivalence over

emotional expression), mediation of CBT by improved cognitive and behavioral coping (decreased catastrophizing and increased pain coping skills), and mediation of both treatments by strength of the working alliance. Finally, the data are used to test whether higher baseline depression and anxiety predict response to EAET and lower baseline depression and anxiety predict response to CBT.

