Aim 3 (Exploratory): Mediation of the Interventions. This aim pertains to the potential mediating effects of ambivalence over emotional expression and emotional approach coping on the effects of EAET, of pain coping and catastrophizing on CBT, and working alliance on both EAET and CBT. For primary and secondary outcomes at post-treatment, we will test the potential mediators that are assessed concurrently. For the 6-month follow-up evaluation, we will test both the post-treatment and the 6-month follow-up (concurrent) mediators. We will examine the mediators separately, but we also will use multivariate methods (principal component scoring algorithm) to explore whether the potential mediators for each intervention should be combined into composites. We will assess mediation by also using the PROCESS macro developed by Hayes (92, 93).

Sample Size and Power Considerations:

Aim 1: Data from our first two pilot groups showed a mean 1.13-point improvement in BPI mean pain severity under EAET compared to a 0.33-point mean improvement of BPI mean pain severity under CBT, a mean difference of $1.13 - 0.33 = 0.80$ points. Using a sample size of $n = 60$ per group and assuming the same SDs, there is 80% power to confirm mean differences as small as 0.70 points using the usual two-sided $\alpha = 0.05$ significance level. In our pilot, only six of 32 participants were lost to follow-up after

completing baseline assessments and randomization. We estimate at least this dropout rate for the proposed study and possibly up to 25% of participants (based on previous studies, e.g., (16)). We therefore will need to enroll at least $60/0.75 = 80$ participants per group or 160 participants total.

Aim 2: A sample size of $n = 60$ has 80% power ($\alpha=0.05$) for confirming correlations as small as $r = 0.35$ (in absolute value) using the usual $\alpha = 0.05$ significance level. Our pilot data shows that the correlation between anxiety and pain change in the EAET group was $r = -0.40$, and the correlation between anxiety and pain change in the CBT group was $r = 0.53$, both well within this margin. Based on the findings of Burger, et al. (23), we anticipate a possibly larger correlation between depression and reduction in pain than found in our pilot groups. We believe that correlations between pain severity change and depression and anxiety also may be even larger, given the large variation in the pilot sample.

Dropouts:

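### Baseline and randomization happen at each Veteran's enrolment, but therapy runs in paired groups of eight with no limit on the gap, so the first-enrolled Veteran's baseline could be about 7.5–15 weeks old at group session 1

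*Combined protocol and SAP*

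**What the plan says.** Section 5.3 sets the order for each Veteran at the in-person enrolment meeting. Consent comes first; "Baseline assessments are then completed"; then "Finally, the Veteran is randomized and scheduled for an individual preparatory session based on treatment assignment (described below".

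Section 5.1 describes delivery: "Group sessions consist of small groups of eight Veterans", and "Each EAET group at a time runs concurrently with one CBT group throughout the study". Section 5.6 gives each arm one individual session and eight group sessions (weekly in EAET, with CBT timing matched to it). The content is sequential, from rationale in session 1 to review and planning in session 8.

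Section 5.2 builds the total as "2 treatment conditions x 10 groups x 8 Veterans = 160" and states that "we have a similar recruitment schedule of approximately 1-2 Veterans per week". Its payment text carries the only week labels: "After completing posttreatment questionnaires (Week 9), participants will receive" a payment, and the six-month questionnaires are placed at Week 39. Week 0 is not defined.

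Table 2 (section 5.5) schedules the BPI and the PROMIS measures at baseline, post-treatment and six months only. The primary outcome is the BPI severity change between the first two of these, and section 5.7 models change from baseline directly. The documents give no maximum interval from baseline to first session, no rule for when a group starts and no method of randomization.

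**The concern.** Veterans are enrolled singly but treated in cohorts. Taken together, sections 5.1, 5.2 and 5.3 leave an untreated interval between baseline and group therapy. It is longest for those enrolled first and close to nil for those enrolled last. Four things are at stake.

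- **Primary change score.** It would include natural fluctuation in pain over a wait that differs between Veterans. Section 5.4 permits any medication and other non-psychotherapy pain treatment, and records these only at the three assessments, so a co-treatment begun during the wait also falls inside the outcome window.
- **Within-arm improvement.** Each arm's reported gain would be partly pre-treatment drift.
- **Aim 2.** Baseline anxiety and depression are the moderators, and for early enrollees they may be weeks out of date when therapy begins.
- **Retention.** A Veteran who withdraws while waiting is already randomized. Section 5.8 stops data collection at withdrawal, so that Veteran enters the intention-to-treat set untreated and without a post-treatment value.

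**Working it through.** **Inputs.** Group size 8 and concurrent pairs (5.1), so 16 Veterans per pair. Planned rate r = 1 to 2 per week, both arms together (5.2). Pilot rate 48/30 = 1.6 per week (5.2). Therapy is 1 individual plus 8 weekly group sessions, about 9 weeks (5.6).

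**The plan's own figures reproduce.** 2 × 10 × 8 = 160. Table 1 gives 24 + 24 + 16 + 16 = 80 per arm, hence 160. The pilot rate of 1.6 lies inside the stated 1 to 2.

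**Waiting time.** Assume even arrivals and a start when the 16th Veteran is enrolled. The k-th enrolled waits (16 − k)/r weeks, so the first waits 15/r. The mean over the pair is (0 + 1 + … + 15)/16 ÷ r = 7.5/r.

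| Rate per week | Time to fill, 16/r | First enrolled, 15/r | Mean, 7.5/r | Share waiting 8 weeks or more |
|---|---|---|---|---|
| 2 | 8.0 | 7.5 | 3.8 | 0/16 = 0% |
| 1.6 | 10.0 | 9.4 | 4.7 | 3/16 = 19% |
| 1 | 16.0 | 15.0 | 7.5 | 8/16 = 50% |

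**Random arrivals.** A simulation with Poisson arrivals and balanced blocks gives an average oldest baseline of 7.5, 9.4 and 15.0 weeks at 2, 1.6 and 1 per week, matching the table. Under simple randomization one arm fills later than the other, and the oldest baseline averages 9.0, 11.3 and 18.2 weeks (mean wait 5.0, 6.3 and 10.2). Both allocation methods are assumptions.

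**Table 1 as a rate.** Spreading 48 or 32 Veterans evenly over 52 weeks would give 0.92 or 0.62 per week and longer waits. That departs from the stated rate, so I do not use it.

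**Week labels.** One individual plus eight weekly sessions fits Week 9 if week 0 is the start of therapy. Week 39 is 39 − 9 = 30 weeks after Week 9, whereas six months is about 26 weeks, which would be Week 35.

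**The case against.** **No start rule is given.** This is the strongest objection, and it stands as a limit on the finding. Nothing says that therapy waits for full groups. The individual session is part of treatment and is scheduled at randomization. Enrolment visits might be clustered before each start, and Table 1's yearly totals per arm are multiples of eight, so enrolment was planned in whole groups. Even so, starting short would depart from groups of eight, and sequential content makes rolling entry unlikely. An early individual session does not refresh the BPI; it only moves the gap to before group session 1. Clustering is stated nowhere, and it is what the fix would write down.

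**The wait as 8 to 16 weeks.** A reader might take this from the recruitment rate. It is the time to fill a pair and not the age of a baseline. At 2 per week, with even arrivals, nobody waits 8 weeks.

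**Week 9 before most of the therapy.** A reader might infer this by counting from enrolment. The documents do not support it: section 5.2 labels that visit as post-treatment, and nine weekly sessions fit a count from the start of therapy. What remains is that week 0 is undefined.

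**A power figure.** With change-score variance proportional to 2(1 − ρ), an assumed fall in the baseline-to-post-treatment correlation from 0.7 to 0.6 multiplies the variance by 0.8/0.6 = 1.33 and moves the detectable difference from 0.70 to 0.70 × √1.33 = 0.81. A fall from 0.6 to 0.5 gives 0.70 × √1.25 = 0.78. Neither fall comes from the documents. Section 5.7 carries over the pilot SDs, and the pilot also randomized before treatment in groups at a similar pace, so those SDs may already contain wait-related noise.

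**Attrition is budgeted.** In the pilot "only six of 32 participants were lost to follow-up after" baseline and randomization, which is 6/32 = 19%, and the plan allows 25% (60/0.75 = 80 per arm). That covers the numbers. It does not supply the missing outcomes of Veterans who leave before treatment.

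**Conclusion.** The point holds as a design weakness worth correcting. Baseline and randomization are tied to individual enrolment, treatment to a cohort start, and nothing bounds the interval between them. At the stated recruitment rate the first-enrolled Veteran's baseline would be about 7.5 to 15 weeks old at group session 1, and the average about 4 to 7.5 weeks. For early enrollees the untreated interval could therefore rival or exceed the roughly nine weeks of therapy. These figures assume even arrivals, balanced allocation and a start when 16 are enrolled; simple randomization would lengthen them.

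A reader might infer that the treatment comparison is biased. The documents do not support that as the main effect: the groups run concurrently, so the wait should be similar in the two arms on average. The cost falls on precision, on the interpretation of each arm's improvement, on the currency of the moderators and on retention after randomization. Its effect on power is of unknown size.

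**What to change.** 1. Keep screening continuous. For each paired start, complete the baseline battery and then randomize within a short stated window before the individual sessions (for example 2 weeks), allocating 8:8 within the cohort of 16.
2. At that visit, recheck the eligibility criteria that carry a time limit, such as CBT for pain in the past 3 months and suicide or violence risk in the past 6 months (section 5.4).
3. If consent is taken earlier, still defer both baseline and randomization to the window. Do not repair a stale baseline by repeating the BPI after randomization. A self-report given once the Veteran has been booked into an assigned arm can be coloured by that knowledge, and it would open a route to between-arm bias that the present order avoids.
4. State when a pair may start, define week 0, time the post-treatment visit from group session 8 and the follow-up from post-treatment, and reconcile Week 39 with the six-month label.

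**Cost.** This is mainly wording and scheduling, with no added questionnaires. Some screened Veterans will lose interest before randomization, which slows accrual a little but leaves the intention-to-treat set intact. Up to 16 baseline visits fall into a short period, and the documents do not show whether current staffing can absorb that. Taking consent early adds a contact.

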5.4 Inclusion/Exclusion Criteria

Inclusion Criteria:

Eligible Veterans are age 60 to 95 years old and have had at least 3 months of musculoskeletal pain, including the following conditions most likely to benefit from psychosocial intervention based on previous research (28):

- regional pain syndromes (e.g., low back, neck, leg, or pelvic pain, or temporomandibular joint disorders);
- widespread pain syndromes (e.g., fibromyalgia);
- whiplash;
- tension headaches; or
- any combination of these disorders.

Exclusion Criteria:

We exclude the following conditions:

- Confirmed hip or knee osteoarthritis without other musculoskeletal pain complaints;

- Leg pain greater than back pain only without other musculoskeletal pain complaints (to exclude radiculopathy in isolation);
- EMG-confirmed “tunnel” syndromes (e.g., carpal or tarsal tunnel syndrome) only without other musculoskeletal pain complaints;
- Autoimmune disease that typically generates pain (e.g., systemic lupus erythematosus, rheumatoid arthritis, inflammatory bowel disease, ankylosing spondylitis);
- Cancer pain, sickle cell disease, neuralgias (e.g., trigeminal neuralgia), burn pain, infection associated with pain (e.g., vertebral infection), cauda equina syndrome, gout, migraine or cluster headaches without additional musculoskeletal pain complaints;
- Uncontrolled severe psychiatric disorder including current psychotic disorder or severe mood disorder not controlled with medications (e.g., schizophrenia or bipolar I disorder), dissociative identity disorder, or active suicide/violence risk in the past 6 months;
- Substantial cognitive impairment or dementia (Mini-Mental State Exam (78) score ≤ 24);
- Active severe alcohol or substance use disorder that inhibits the participant’s ability to attend session or participate in homework;
- Currently with pain-related litigation or applying for pain-related compensation or compensation increase, or undergoing compensation re-evaluation (e.g., applying for VA service connection or service connection increase for pain);
- Patients who are currently receiving CBT or EAET psychotherapy treatment for pain;
- Patients who have received CBT for pain in the past 3 months;
- Unable to fluently read/converse in English;
- Planning to move from the area in the next 6 months.

Medications/Other Treatments:

Consistent with other trials of psychosocial interventions for chronic pain (23, 24), participants will not be excluded due to using any medications at any dose, or for pursuing other non-psychotherapy treatment options for chronic pain (e.g., trigger point injections, physical therapy), or for participating in psychotherapy for another condition (e.g., depression, insomnia). However, current medications and dosages, other treatments, and presence of psychotherapy for other conditions are recorded at baseline, post-treatment, and follow-up visits for monitoring purposes and possible post-hoc analyses.

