In contrast, promising research on an innovative psychological treatment, Emotional Awareness and Expression Therapy (EAET), has shown that some chronic pain patients who receive psychotherapy can achieve medium-to-large benefits on pain severity and other outcomes (23-25). EAET is grounded in exposure-based, experiential, and psychodynamic theories and uses innovative emotion-focused techniques to reduce stress and alter central nervous system processes to reduce or eliminate pain (26). A recent large study, PAST-FM, showed significantly greater rates of 50% pain reduction at both post-treatment and 6-month follow-up for EAET compared to either CBT or education control for adult outpatient non-Veterans with fibromyalgia, a disorder of widespread musculoskeletal pain (27). Additionally, in a series of 72 adult patients with chronic musculoskeletal pain conditions who received EAET, two-thirds of patients achieved at least 30% pain reduction and one-third of patients had at least 70% pain reduction—rates of success that are almost never found with CBT (23). Finally, in our pilot project at VA Greater Los Angeles, older Veterans with chronic musculoskeletal pain who received EAET had a reduction in mean pain severity nearly three times greater than those who received CBT: -1.44 versus -0.39.

Rationale for the Population Chosen:

In order to begin the process of optimizing the psychosocial treatment of chronic pain at VA, the proposed research uses a sample of Veterans likely to respond to psychotherapy, older Veterans. First, according to theory, developmentally older adults are at a phase of life in which they often desire to reflect and process issues, such as is the case in psychotherapy (31). Second, group cognitive behavioral and psychodynamic psychotherapy treatments have been found to be beneficial in depressed older adult Veterans and depressed caregivers in two separate trials at the Palo Alto VA (32, 33). Finally, psychotherapy is suited to older adult Veterans because older adults have been shown to overwhelmingly prefer psychosocial treatments of any modality to pharmacologic treatments (34, 35).

Individual Differences in Response to Cognitive/Behavioral and Emotional Interventions and Proposed Moderators:

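### Completed EAET has no look-back and pilot EAET recipients are not excluded, so previously treated Veterans can be randomized and modestly dilute the EAET–CBT contrast

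*Combined protocol and SAP*

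**What the plan says.** The exclusion list in section 5.4 has two lines on earlier psychotherapy for pain. The first covers both therapies, but only while treatment is ongoing: "Patients who are currently receiving CBT or EAET psychotherapy treatment for pain". The second looks back in time, but for CBT alone: "Patients who have received CBT for pain in the past 3 months". No line deals with completed EAET, and no section excludes people who took part in the pilot.

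The pilot delivered EAET locally to the same kind of patient. Section 2.0 reports its results for Veterans treated there: "in our pilot project at VA Greater Los Angeles, older Veterans with chronic musculoskeletal pain who received EAET". Section 5.2 says that the investigators partnered with several clinics "for our pilot, and plan to use these sites for this project as well", and that in the pilot "we were able to recruit 48 participants from our clinical sites in 30 weeks".

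On data capture, the paragraph on medications and other treatments in section 5.4 says that current medications, "other treatments, and presence of psychotherapy for other conditions are recorded at baseline, post-treatment, and follow-up visits". Past EAET or CBT for pain is not named there. It is also not among the baseline characteristics that section 5.7 lists for comparison and possible adjustment.

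**The concern.** By setting a look-back for CBT, the plan accepts that recently completed therapy matters. It gives no reason for treating EAET differently. A former pilot participant whose pain persists could see a flyer in one of the same clinics and refer himself or herself. If randomized to EAET, that person repeats a course already taken. If randomized to CBT, that person may still be doing EAET exercises, because the last EAET group session (section 5.6) ends with a written plan for continued practice.

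In either case the participant may show less of the difference between therapies than a newly treated one. Randomization spreads such people evenly over the arms on average, so the issue is a smaller expected contrast and some lost power, not selection bias. Section 5.6 guards against mixing of therapies on the therapists' side, through one condition per interventionist and fidelity checks. There is no matching screen on the patients' side. Because past EAET is not named among the items recorded, affected participants might not be identifiable in the analysis.

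**Working it through.** **Inputs.** From section 5.7: 60 evaluable per group; 80% power for 0.70 points; two-sided alpha 0.05; dropout up to 25%; and the pilot contrast, "a mean difference of $1.13 - 0.33 = 0.80$ points". From section 5.2: 48 pilot recruits. Not in the documents, so assumed: the SD, the share *f* of participants with prior EAET (taken to be the same among those evaluable), and the fraction *r* of the arm difference that they retain.

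**The plan's own figure.** 60 / 0.75 = 80 per group, or 160 in total. This reproduces.

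**Implied SD.** The plan refers to pilot SDs without giving them. Solving its power statement:

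0.70 = (1.960 + 0.842) × SD × √(2/60), so SD = 0.70 / (2.802 × 0.1826) ≈ 1.37.

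A noncentral t calculation gives 1.36. With this SD the plan has 80% power for 0.70 by construction, and 89% for 0.80.

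**Dilution.** Expected difference = δ × [1 − f × (1 − r)]. The worst case used here is r = 0.

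| Prior EAET, of 160 | True 0.80 becomes | Power | True 0.70 becomes | Power |
|---|---|---|---|---|
| 0 | 0.80 | 89% | 0.70 | 80% |
| 4 (2.5%) | 0.78 | 88% | 0.682 | 78% |
| 8 (5%) | 0.76 | 86% | 0.665 | 76% |
| 16 (10%) | 0.72 | 82% | 0.63 | 71% |
| 24 (15%) | 0.68 | 78% | 0.595 | 66% |

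For example, at 10%: 0.80 × (1 − 0.10) = 0.72.

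**Milder assumption.** With r = 0.5 and f = 15%, the differences are 0.80 × 0.925 = 0.74 and 0.70 × 0.925 ≈ 0.647, with power of 84% and 74%.

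**Break-even.** To bring 0.80 down to the stated detectable 0.70 with r = 0, f must be 1 − 0.70/0.80 = 12.5%, which is 20 of 160.

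**Plausible upper end.** The 48 pilot recruits cover both arms. If the split was 1:1, about 24 had EAET, so the last table row corresponds to the whole pilot EAET arm re-enrolling.

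**The case against.** The strongest reply is that hardly anyone is affected. The documents name no local source of EAET other than the pilot. The list of alternatives in section 6.0 includes CBT for chronic pain but not EAET, and section 2.0 leaves the introduction of EAET across the VA to future research. A look-back only for the therapy in routine use is therefore understandable, and no section says that any pilot participant will return. All of this stands, and it limits the size of the problem. It does not close the route, since the pilot clinics are to be used again.

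Second, the primary outcome is change from baseline. Lasting benefit from earlier EAET is already in the baseline score, so continued use of EAET skills does not by itself add change in the CBT arm. This weakens the contamination argument. Less room to improve, and a repeated course, remain.

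Third, zero arm difference is an extreme assumption, and 0.70 is the smallest detectable difference, not the planning value. From 0.80, power stays above 80% even at 10% re-entry. From the larger pilot contrast in section 2.0 (1.44 − 0.39 = 1.05), 10% re-entry would leave about 96.5%, if the SD is the same. This is fair, and it is why both starting points are shown.

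A reader might go further in three ways that the documents do not support:

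- That pilot EAET recipients could enter immediately after finishing. The documents give no pilot dates, so the interval is unknown.
- That data from re-enrolled pilot participants would not be new evidence. They would be newly randomized and give new baseline and outcome scores, and no section pools pilot data into the trial.
- That all 48 pilot recruits carry prior EAET exposure. That number covers both arms.

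**Conclusion.** The gap is real and its likely effect is small. As written, section 5.4 admits Veterans who have completed EAET, including in the pilot, to either arm. Any resulting dilution pulls the estimate towards no difference; it does not favor EAET or inflate the type I error.

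Under the worst-case assumption the loss is about 2 percentage points of power for four such participants. For 24 it is about 12 points from a true 0.80 (89% to 78%, before rounding 89.3% to 77.7%) and about 14 points from 0.70 (80% to 66%). These figures rest on a back-solved SD, an unknown re-entry share, an assumed 1:1 pilot split and no retained arm difference. The documents show that dilution is possible, not that it will occur. The point is minor, but it is worth correcting because the correction is so cheap.

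**What to change.** - In section 5.4, exclude anyone who has previously received EAET for pain, including in the pilot, with no time limit. At the least, exclude pilot participation explicitly. This is the part that does the work: without pilot dates, a 3-month window may catch none of them.
- Extend the existing 3-month look-back line to name both CBT and EAET, or state why the two therapies are treated differently.
- For anyone already enrolled, record prior EAET or CBT for pain and pilot participation, and prespecify in section 5.7 a sensitivity analysis of the primary outcome without those participants.

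The cost is two lines of eligibility text, one baseline item and one extra analysis. At most 48 potential recruits are lost, or about 24 if only EAET recipients are barred and the pilot split was 1:1. A prior-EAET rule has one advantage over a blanket pilot exclusion: it does not bar pilot CBT participants while the plan admits other Veterans whose CBT ended more than 3 months ago.
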